2	Moderate; minimal, local, or non-invasive intervention indicated; or limiting age-appropriate instrumental activities of daily living ^a
3	Severe or medically significant, but not immediately life-threatening; hospitalization or prolongation of hospitalization indicated; disabling; or limiting self-care activities of daily living ^{b,c}
4	Life-threatening consequences or urgent intervention indicated d
5	Death related to adverse event ^d

NCI CTCAE = National Cancer Institute Common Terminology Criteria for Adverse Events.

Note: Based on the most recent version of NCI CTCAE (v5.0), which can be found at:

http://ctep.cancer.gov/protocolDevelopment/electronic_applications/ctc.htm

- a. Instrumental activities of daily living refer to preparing meals, shopping for groceries or clothes, using the telephone, managing money, etc.
- b. Examples of self-care activities of daily living include bathing, dressing and undressing, feeding oneself, using the toilet, and taking medications, as performed by patients who are not bedridden.
- c. If an event is assessed as a "significant medical event," it must be reported as a serious adverse event
- d. Grade 4 and 5 events must be reported as serious adverse events

f. Pregnancy

If a female subject becomes pregnant while receiving the study drug or within 6 months after the last dose of study drug, or if the female partner of a male study subject becomes pregnant while the study subject is receiving the study drug or within 6 months after the last dose of study drug, a report should be completed and expeditiously submitted to Genentech, Inc. Follow-up to obtain the outcome of the pregnancy should also occur. Abortion, whether accidental, therapeutic, or spontaneous, should always be classified as serious, and expeditiously reported as an SAE. Similarly, any congenital anomaly/birth defect in a child born to a female subject exposed to the study drug should be reported as an SAE.

Additional information on any ocrelizumab-exposed pregnancy and infant will be requested by Genentech/Roche Drug Safety at specific time points (i.e. after having received the initial report, at the end of the second trimester, 2 weeks after the expected date of delivery, and at 3, 6, and 12 months of the infant's life).

g. Post-Study Adverse Events

The investigator should expeditiously report any SAE occurring after a subject has completed or discontinued study participation if attributed to prior ocrelizumab exposure. If the investigator should become aware of the development of cancer or a congenital anomaly in a subsequently conceived offspring of a female subject who participated in the study, this should be reported as an SAE adequately to Genentech drug Safety during follow up period

h. Case Transmission Verification of Single Case Reports

The Sponsor agrees to conduct the Case Transmission verification to ensure that all single case reports have been adequately received by Genentech via the sponsor emailing Genentech a Quarterly line-listing documenting single case reports sent by the sponsor to Genentech in the preceding time period.

The periodic line-listing will be exchanged within seven (7) calendar days of the end of the agreed time period. Confirmation of receipt should be received within the time period mutually agreed upon.

If discrepancies are identified, the Sponsor and Genentech will cooperate in resolving the discrepancies. The responsible individuals for each party shall handle the matter on a case-by-case basis until satisfactory resolution. The sponsor shall receive reconciliation guidance documents within the 'Activation Package'.

Following Case Transmission Verification, single case reports which have not been received by Genentech shall be forwarded by the sponsor to Genentech within five (5) calendar days from request by Genentech.

At the end of the study, a final cumulative Case Transmission Verification report will be sent to Genentech

i. AEs of Special Interest (AESIs)

AESIs are a subset of Events to Monitor (EtMs) of scientific and medical concern specific to the product, for which ongoing monitoring and rapid communication by the Investigator to the Sponsor is required. Such an event might require further investigation in order to characterize and understand it. Depending on the nature of the event, rapid communication by the trial Sponsor to other parties (e.g., Regulatory Authorities) may also be warranted.

Adverse events of special interest for this study include the following:

- Cases of potential drug-induced liver injury that include an elevated ALT or AST in combination with either an elevated bilirubin or clinical jaundice, as defined by Hy's law:
 - o Treatment-emergent ALT or AST 2 3 2 ULN in combination with total bilirubin 2 2 ULN
 - o Treatment-emergent ALT or AST 2 3 2 ULN in combination with clinical jaundice

• Data related to a suspected transmission of an infectious agent by the study drug, as defined below:

 Any organism, virus, or infectious particle (e.g., prion protein transmitting transmissible spongiform encephalopathy), pathogenic or non-pathogenic, is considered an infectious agent. A transmission of an infectious agent may be suspected from clinical symptoms or laboratory findings that indicate an infection in a patient exposed to a medicinal product. This term applies only when a contamination of the study drug is suspected.

j. Exchange OF SINGLE CASE REPORTS

The sponsor will be responsible for collecting all protocol-defined Adverse Events (AEs)/Serious Adverse Events (SAEs), AEs of Special Interest (AESIs), Special Situation Reports (including pregnancy reports) and Product Complaints (with or without an AE) originating from the Study for the Product.

Investigators must report all the above mentioned single case reports adequately to Genentech within the timelines described below. The completed MedWatch or CIOMS I form or Genentech approved reporting forms should be faxed/emailed immediately upon completion to Genentech at the following contacts:

All protocol-defined AEs, SAEs, AESIs, Special Situation Reports (including pregnancy reports) and Product Complaints with an AE should be sent to:

[contact]

Email: [contact]

All Product Complaints without an AE should be sent to:

Email: [contact]

It is understood and agreed that the Sponsor will be responsible for the evaluation of AEs/SAEs, AESIs, Special Situation Reports (including pregnancy reports) and Product Complaints (with or without an AE) originating from the study.

These single case reports will be exchanged between the parties as outlined below so that regulatory obligations are met.

Serious adverse events (SAEs), pregnancy reports (including pregnancy occurring in the partner of a male study subject) AEs of special interest (AESIs) and Special Situation Reports, where the patient has been exposed to the Genentech Product, will be sent on a MedWatch form or CIOMS I form or on Genentech approved reporting forms to Genentech Drug Safety. Transmission of these reports (initial and follow-up) will be either electronically or by fax and within the timelines specified below:

• SADRs

Serious AE reports that are related to the Product shall be transmitted to Genentech within fifteen (15) calendar days of the awareness date.

Other SAEs

Serious AE reports that are unrelated to the Product shall be transmitted to Genentech within thirty (30) calendar days of the awareness date.

• AESIs

AESIs shall be forwarded to Genentech within fifteen (15) calendar days of the awareness date.

• Special Situation Reports

Pregnancy reports

While such reports are not serious AEs or Adverse drug Reactions (ADRs) per se, as defined herein, any reports of pregnancy (including pregnancy occurring in the partner of a male study subject), where the fetus may have been exposed to the Product, shall be transmitted to Genentech within thirty (30) calendar days of the awareness date. Pregnancies will be followed up until the outcome of the pregnancy is known, whenever possible, based upon due diligence taken to obtain the follow-up information.

• Other Special situation reports

In addition to all SAEs, pregnancy reports and AESIs, the following Special Situations Reports should be collected even in the absence of an Adverse Event and transmitted to Genentech within thirty (30) calendar days:

• Data related to the Product usage during pregnancy or breastfeeding

• Data related to overdose, abuse, off-label use, misuse, inadvertent/erroneous administration, medication error (including potentially exposed in case of medication errors or intercepted medication errors) or occupational exposure, with or without association with an AE/SAE unless otherwise specified in the protocol

- Lack of therapeutic efficacy
- Drug interaction

• Use of a Medicinal Product in a Pediatric and Elderly population (in addition, reasonable attempts should be made to obtain and submit the age or age group of the patient, in order to be able to identify potential safety signals specific to a particular population)

• Product Complaints

All Product Complaints (with or without an AE) shall be forwarded to Genentech within fifteen (15) calendar days of the awareness date.

A Product Complaint is defined as any written or oral information received from a complainant that alleges deficiencies related to identity, quality, safety, strength, purity, reliability, durability, effectiveness, or performance of a product after it has been released and distributed to the commercial market or clinical trial.

MEDWATCH 3500A REPORTING GUIDELINES

In addition to completing appropriate patient demographic (Section A) and suspect medication information (Section C & D, the report should include the following information within the Event Description (section B.5) of the MedWatch 3500A form:

• Protocol number and title description

- Description of event, severity, treatment, and outcome if known
- Supportive laboratory results and diagnostics (Section B.6)

• Investigator's assessment of the relationship of the adverse event to each investigational product and suspect medication

Follow-Up Information

Additional information may be added to a previously submitted report by any of the following methods:

• Adding to the original MedWatch 3500A report and submitting it as follow-up

• Adding supplemental summary information and submitting it as follow-up with the original MedWatch 3500A form

• summarizing new information and faxing it with a cover letter including patient identifiers (i.e. D.O.B. initial, patient number), protocol description and number, if assigned, brief adverse event description, and notation that additional or follow-up information is being submitted (The patient identifiers are important so that the new information is added to the correct initial report)

Reporting to Regulatory Authorities, Ethics Committees and Investigators

Genentech as the Marketing Authorization Holder will be responsible for the reporting of individual case safety reports from the study to the regulatory authority in compliance with applicable regulations.

The sponsor will be responsible for the expedited reporting of safety reports originating from the Study to the EMA through Eudravigilance Clinical Trial Module (EVCTM), where applicable.

The sponsor will be responsible for the distribution of safety information to Site IRB:

[name]

Faxes:[contact] or [contact]

For questions related to safety reporting, please contact Genentech/Roche Drug Safety:

[contact]

[contact] or [contact]

Other Reports

The sponsor will forward a copy of the Publication to Genentech/Roche upon completion of the Study.

STUDY CLOSE-OUT

Any literature articles that are a result of the study should be sent to Genentech/Roche. Copies of such reports should be mailed to the assigned Clinical Operations contact for the study:

[contact] , your Genentech MSL and to Genentech Drug Safety CTV oversight mail box at: [contact]

QUERIES

Queries related to the Study will be answered by the sponsor. However, responses to all safety queries from regulatory authorities or for publications will be discussed and coordinated between the Parties. The Parties agree that Genentech/Roche shall have the final say and control over safety queries relating to the Product. The sponsor agrees that it shall not answer such queries from regulatory authorities and other sources relating to the Product independently but shall redirect such queries to Genentech/Roche.

Both Parties will use all reasonable effort to ensure that deadlines for responses to urgent requests for information or review of data are met. The Parties will clearly indicate on the request the reason for urgency and the date by which a response is required.

SAFETY CRISIS MANAGEMENT

In case of a safety crisis, e.g., where safety issues have a potential impact on the indication(s), on the conduct of the Study, may lead to labeling changes or regulatory actions that limit or restrict the way in which the Product is used, or where there is media involvement, the Party where the crisis originates will contact the other Party as soon as possible.

The Parties agree that Genentech/Roche shall have the final say and control over safety crisis management issues relating to the Product. The sponsor agrees that it shall not answer such queries from media and other sources relating to the Product but shall redirect such queries to Genentech/Roche.

DISCLOSURE AND PUBLICATION OF DATA

Subject medical information obtained by this study is confidential, and disclosure to third parties other than those noted below is prohibited.

Upon the subject's permission, medical information may be given to his or her personal physician or other appropriate medical personnel responsible for his or her welfare.

Data generated by this study must be available for inspection upon request by representatives of national and local health authorities, Genentech, and the IRB for each study site, if appropriate.

The results of this study may be published or presented at scientific meetings. The Sponsor will comply with the requirements for the publication of study results.

Additionally, Section 801 of the Food and Drug Administration Amendments Act (FDAAA 801) (PDF) requires Responsible Parties to register and submit summary results of clinical trials with ClinicalTrials.gov. The law applies to certain clinical trials of drugs (including biological products) and medical devices. (refer to FDAAA 801 Requirements to learn about Responsible Party, Applicable Clinical Trials, and deadlines for registration and results submission)

RETENTION OF RECORDS

U.S. FDA regulations (21 CFR §312.62[c]) require that records and documents pertaining to the conduct of this study and the distribution of investigational drug, including CRFs, consent forms, laboratory test

results, and medication inventory records, must be retained by the Principal Investigator for 2 years after marketing application approval. If no application is filed, these records must be kept 2 years after the investigation is discontinued and the U.S. FDA and the applicable national and local health authorities are notified. Genentech will notify the Principal Investigator of these events.

For studies conducted outside the United States under a U.S. IND, the Principal Investigator must comply with U.S. FDA IND regulations and with the record retention policies of the relevant national and local health authorities.

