Screening visit: PI or designee will explain the study consent to study participants, and the study visit assessments will occur after the study participants sign the consent form. Screening visit procedures include review of eligibility criteria, physical exam, EDSS, collecting vitals, and blood draw (for collecting PBMCs), and completion of Neuro-QoL adult item banks. Study participants will be enrolled into the study after the study physician confirms participants' eligibility to move forward with the study.

RATIONALE FOR STUDY DESIGN

The reason we chose a single arm, open label study, as opposed to a blinded controlled study is because the latter does not help with answering our research question. Our research question is if two courses of treatment with anti-CD20 antibody, ocrelizumab corrects the B-cell tolerance defect seen in patients with relapsing-remitting multiple sclerosis.

OUTCOME MEASURES PRIMARY OUTCOME MEASURE

Assessment of T and B-cell phenotypes and function at baseline and 18-24 months post-B-cell depletion:

The assessment T and B-cell phenotypes and function and analysis of the central and peripheral B-cell tolerance checkpoints, as well as measurement of cytokines will be done at [name] at Johns Hopkins University. 50 milliliters of blood will be drawn from participants before start of the treatment with ocrelizumab (at the screening visit) and 12 or 18 months after the second course of ocrelizumab infusion (month 18 or 24 of the study) and will be sent to [name] for the analyses explained below. We will investigate the T and B-cell phenotypes in fresh blood samples from 10 individuals with MS pre-treatment and after they repopulate their peripheral B-cells likely at either 18 or 24 months' time points. We will follow the frequencies of CD3+CD4+CD25hiCD127loFOXP3+ Tregs, circulating CD3+CD4+CXCR5+PD-1+ Tfh cells increased in several autoimmune diseases, and other CD4+ and CD8+ naïve and memory T cell subpopulations. We will also assess the production of several cytokines including IL-10, IL-17, and IFN-gamma by Tregs and other T cell subsets after activating PBMCs with phorbol-12-myristate-13-acetate (PMA) and ionomycin for 4 hours in the presence of GolgiStop (BD

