Protocol-specified therapy may be discontinued for any of the following reasons:

- Unacceptable toxicity
- Patient election to discontinue therapy (for any reason)
- Physician's judgment

SUBJECT DISCONTINUATION

Treatment stop rules: Stopping the study is equivalent to restarting the B-cell depleting antibody (i.e. ocrelizumab) or another DMT, if there is medical contraindication to the continued use of ocrelizumab (e.g. development of allergic or severe infusion reactions during the last infusion). The followings are the criteria for restarting the DMT (stopping the study).

1. A clinical relapse, affecting optic nerves (with worst visual acuity of 20/50 or less) or causing motor weakness, ataxia, bladder or bowel symptoms. Pseudo-relapses are not uncommon among patients with MS. When in doubt, the PI will use MRI to confirm development of new lesions corresponding to patient's symptoms (based on the possible localization of the symptoms).

2. Development of two new T2 hyperintense lesions or two gadolinium enhancing lesions on any MRI after the baseline MRI. The baseline MRI was defined the MRI that is obtained after three months subsequent to the first ocrelizumab infusion.

Termination rule

If four patients during the study required retreatment with ocrelizumab (or another DMT), we will terminate the study (i.e. will offer all participants the choice to resume their DMT).

STUDY DISCONTINUATION

Genentech Study Center, and the Principal Investigator has the right to terminate this study at any time. Reasons for terminating the study may include the following:

• The incidence or severity of adverse events in this or other studies indicates a potential health hazard to subjects

- Subject enrollment is unsatisfactory
- Data recording are inaccurate or incomplete
- Study protocol not followed

STATISTICAL METHODS

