We will describe the demographic, clinical characteristics and MRI data of all participants before treatment with the B-cell depleting agent. Using paired t-tests, we will compare the frequency of autoreactive mature naïve B-cells, Treg and Tfh cells and cytokine production before treatment with ocrelizumab and after the B-cell repopulation. We will report the proportion of participants who experience the return of the disease activity and the time to failure event, using a Kaplan-Meyer curve. Proportion of patients with clinical relapse, new MRI activity or disability progression will separately be reported. Quality of life data will be analyzed using linear mixed effect models.

To look at the association between long-term response to B-cell depletion therapy and autoreactivity of B-cells at different stages of development, we will use logistic regression and Cox proportional hazards models with failure or time-to-failure event as the outcome variable and the above-mentioned proportion of auto-reactive B-cells at different stages of development and the change in proportions before and after treatment as the predictor variables. Failure event as defined by the return of disease activity after the third month post-first-infusion, objectively demonstrated by development of new T2 hyperintense lesions or Gd-enhancing lesions on the MRI or a clinical relapse that is confirmed with an objective change in the neurological examination or a corresponding new or enhancing lesion on the MRI that is obtained after the onset of symptoms.

Missing Data

Because of the small sample size and close follow-up, we do not expect to encounter missing data problem. Also, each participant will be his/her own control and no between-patient comparison will be made.

Determination of Sample Size

Patients' numbers are also based on our previous studies of central and peripheral B-cell checkpoints in patients with autoimmune diseases and healthy control subjects in which we had found that the frequency of autoreactive mature naïve B-cells was 48.9±3.06% in patients and 20.1±0.9% in healthy donors. Assuming that the frequency of autoreactive cells among post-treatment repopulated B-cells will be similar to normal controls, our proposed sample size of 10 subjects per group before and after

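### Nothing provides for taking the post-treatment primary blood draw before DMT restarts, so a repopulated participant can lose half of the primary pair

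*Combined protocol and SAP*

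**What the plan says.** Under SUBJECT DISCONTINUATION, the Treatment stop rules state: "Stopping the study is equivalent to restarting the B-cell depleting antibody", or another DMT where ocrelizumab is contraindicated. One participant restarts after a relapse of a listed type, or on the MRI criterion: "Development of two new T2 hyperintense lesions or two gadolinium enhancing lesions on any MRI after the baseline MRI". The Termination rule then acts on the whole study: "If four patients during the study required retreatment with ocrelizumab (or another DMT), we will terminate the study", meaning that the investigators "will offer all participants the choice to resume their DMT".

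The primary outcome compares blood taken at screening with blood taken "after they repopulate their peripheral B-cells likely at either 18 or 24" months (PRIMARY OUTCOME MEASURE). The schedule tables place the second draw at month 18 or, alternatively, month 24. T and B-cell phenotyping is specified in fresh blood. Blood is also stored at screening and months 3, 6, 12 and 18, but it is not named as a substitute for the primary draw.

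STATISTICAL METHODS plans paired t-tests of before against after. It also plans logistic and Cox models of failure that include "the change in proportions before and after treatment as the predictor variables". The Missing Data paragraph expects no missing-data problem. The stop rules, termination rule, schedule and statistical section contain no draw before restart and no end-of-study draw.

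**The concern.** The protocol's own restart rules can remove a primary observation that the plan assumes will be there. The screening half of the pair is already in hand. If ocrelizumab resumes before the second draw, the first repopulation can no longer be observed; if another DMT starts, a later sample reflects that drug as well. Stored blood is not a planned fallback.

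Two routes lead to this loss: individual restarts, which account for most of it, and the study-wide offer at the fourth retreatment. In both, the samples that could be saved are those of participants who have repopulated, have not been drawn and go on to restart. In a study of 10, each lost pair is one tenth of the primary data.

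**Working it through.** **1. The plan's own power figure.** Determination of Sample Size gives 48.9±3.06% against 20.1±0.9%, 10 before and 10 after, two-sided α 0.05, power above 90%. The difference is 48.9 − 20.1 = 28.8 points. The ± is not labelled. As an SD, the pooled SD is √((3.06² + 0.9²)/2) = 2.26 and power is about 1.00. As an SEM, SD = SEM × √m for m source subjects; with m assumed to be 10, 20 or 30, power is at least 0.998. The stated figure reproduces.

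**2. Chance that the termination rule fires.** The documents give no retreatment rate, so 20, 30 and 40% by month 30 are assumed. The protocol's remark that 3-4 participants may have a central tolerance defect, with a less lasting effect, makes 30 to 40% possible but does not predict it. For X ~ Binomial(10, p), P(X ≥ 4) = 1 − Σ(k = 0 to 3) C(10,k) p^k (1−p)^(10−k) = 0.12, 0.35 and 0.62.

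**3. Chance that a draw before restart saves at least one sample.** This was simulated (100,000 runs per setting in the cases where all activity is found at once or only at scheduled MRIs). All of the following are assumptions:
- constant retreatment hazard from month 6 or 12, reaching p at month 30;
- accrual spread over 0, 12 or 24 months;
- repopulation uniform over months 12 to 24;
- draw at month 18 if repopulated by then, otherwise month 24;
- 50 or 100% acceptance of DMT at termination.

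The answer depends strongly on when activity is detected:

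| Detection of activity | 20% retreated | 30% | 40% |
|---|---|---|---|
| Only at scheduled brain MRIs (months 12, 18, 24, 30) | 0 to 0.04 | 0 to 0.15 | 0 to 0.31 |
| Half found between visits | 0.12 to 0.19 | 0.18 to 0.32 | 0.25 to 0.47 |
| All found at once (upper case) | 0.23 to 0.31 | 0.35 to 0.47 | 0.46 to 0.63 |

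In the first row, individual restarts contribute nothing. At month 12 no one has repopulated under these assumptions, and months 18 and 24 are themselves draw visits. The termination step also contributes nothing if all enrol together.

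In the last row, the termination step alone gives only 0.02 to 0.06, 0.08 to 0.18 and 0.17 to 0.35. Mean samples saved per study there are 0.28 to 0.41, 0.46 to 0.77 and 0.64 to 1.21.

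Most lost draws cannot be rescued. Per termination at 30 to 40%, again in the upper case, 2.3 to 3.1 of the retreated participants restart undrawn, but only 0.5 to 0.8 of those have repopulated.

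**4. Effect on the primary test.** Paired power comes from the noncentral t with n − 1 degrees of freedom and noncentrality 28.8 / (SD_d/√n). At within-pair correlation 0 (assumed), SD_d = √(3.06² + 0.9²) = 3.19 if ± is an SD, or 3.19 × √m if it is an SEM; for m = 30 this is 17.5.

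| Pairs left | ± as SD | SEM, m = 10 | SEM, m = 20 | SEM, m = 30 |
|---|---|---|---|---|
| 6 | 1.00 | 1.00 | 0.97 | 0.89 |
| 5 | 1.00 | 1.00 | 0.91 | 0.785 |
| 4 | 1.00 | 0.95 | 0.76 | 0.60 |

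In the upper case, with full acceptance, a terminated study keeps on average 4.8 to 6.2 pairs at 30% retreatment and 4.1 to 5.6 at 40%. With the draw it keeps 5.9 to 7.7 and 5.3 to 7.2.

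**5. Use in the association models.** Failure is broad: "Failure event as defined by the return of disease activity after the third month post-first-infusion", shown by new T2 or enhancing lesions with no minimum number, or by a confirmed relapse. Restart needs two lesions or a listed relapse type. Restart criteria are thus essentially a subset of failure, and a sample taken at an individual restart nearly always follows the failure event.

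**The case against.** The strongest reply is that the text already leaves room. The draw is tied to repopulation and months 18 and 24 are only described as likely, so staff at a single centre with 10 participants could draw early without departing from the protocol. A reader might infer that an early draw is forbidden; the wording does not support that. This part stands, but a permission is not an instruction, and the decision would fall at the moment of a relapse with no agreed definition of repopulation.

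The second reply is that many restarts will be triggered at scheduled MRIs, two of which coincide with the draw. That also stands, and it is why the first row of the detection table is so low. It is not the whole picture, because the protocol allows symptom-driven MRI and makes listed relapses a restart trigger in their own right.

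Third, samples drawn after failure do little for the association analysis. This is correct: a change measured after the event is not a valid predictor of time to that event. The usable gain there comes mainly from participants who have not failed when the study-wide offer is made.

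Fourth, the fresh-blood requirement is stated for phenotyping, not for the antibody-cloning assay behind the power statement. That is a fair limit, but stored blood is still not planned as its source.

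**Conclusion.** The gap is real and minor. Following the plan as written can irrecoverably lose a primary pair, and a cheap instruction would prevent some of those losses. At 20 to 40% retreatment, the chance that it saves at least one sample runs from 0 to 0.63 across the three detection assumptions, with the top of that range an upper case. Retreatment rate, accrual, repopulation timing, acceptance and detection are all assumed, because the documents give none of them.

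A reader might infer that the termination rule defeats the primary comparison. The documents do not support that. Power stays near 1.00 at four pairs if ± is an SD, and is 0.95 if it is an SEM from 10 subjects. It falls to between 0.60 and 0.785 only when four or five pairs remain and the SEM came from about 30 subjects. That is the most pessimistic reading tried, though not a bound.

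A reader might also infer that the study-wide offer selectively removes non-failures. Non-retreated participants may already have failed, for example with a single new lesion, so the direction of any selection is unknown.

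**What to change.** Leave the individual and study-wide safety thresholds unchanged. Add one paragraph to the stop rules and one to the statistical section:

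- **Draw.** Before any DMT restart, individual or at termination, take the planned 50 mL draw from every undrawn participant who may have repopulated, provided care is not delayed. Take it before infusion premedication, which includes methylprednisolone, since entry requires 30 days without steroids. Record any relapse steroids already given.
- **Repopulation.** Confirm it from that sample's own B-cell counts, against a threshold set in advance, for example enough mature naïve cells to yield the 20-30 antibodies the assay needs.
- **Paired comparison.** Include the confirmed samples, record actual time since the second infusion, and add a sensitivity analysis without them.
- **Cox model.** Do not use a before-after change measured after the failure event as a predictor.

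The draw is already planned and only moves earlier. The costs are laboratory processing at short notice, some draws that prove to be too early, and samples that compare less well with scheduled ones, since they may hold more transitional B-cells. A sensitivity analysis on one or two samples cannot settle that comparability question.
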